### **3.2 Secondary Objectives**

The secondary objectives of Aim 1 are to assess the effects of the performance improvement program on pain and individual BPSDs in the PWD, and the use of antipsychotic and analgesic. They will be measured at all four time points (0, 15, 30, and 60 days). BPSD will be measured using the NPI-Q. The type of pain assessment administered to the PWD will depend on their level of cognitive impairment. The level of impairment will be determined by the Quick Dementia Rating System (QDRS) score. The PWD who obtains a score of  $\leq 12$  will receive the Brief Pain Inventory Short Form^103 and those whose score  $\geq 12$  on the QDRS will receive the PAINAD which will be used to measure pain at rest and with movement. All PWD subjects will be assessed for pain during each visit using the respective measure.

The secondary objectives of Aim 2 are to assess the effects of the performance improvement program on informal caregiver burden, depression, and functional health and well-being. The PHQ-9 will be used to measure caregiver depression, the Zarit Burden Interview for caregiver burden and the SF-12 for caregiver health at 0 and 60 days.

The secondary objectives of Aim 3 are to assess the effects of the performance improvement program on the number of outpatient visits and contacts with the primary care provider. These will be measured through interviews at 30 and 60 days with the Resource Utilization Inventory.

## **4 Study Design and Endpoints**

### **4.1 Description of Study Design**

This study will use a blinded cluster randomized controlled trial methodology. Each HHC care team will be randomized to either partake in the DSM-H performance improvement program or provide usual care. The project director based at NYU and RAs at all sites will be blinded to prevent bias in data collection. The study statistician based at NYU will perform the randomization utilizing SAS 9.4 stratified by agency and geographic location. The study PI will relay to the agencies which teams will serve as intervention or control. The study PI and statistician will not collect study data in order to maintain the integrity of the blinding. The potential for contamination between care teams randomized to receive the DSM-H performance improvement program and those who will provide usual care is minimal due to the nature of HHC clinician workflow where minimal time is spent in the office, and different care teams do not generally congregate with each other except during highly structured staff meetings. The investigators considered randomizing by site and using other HHC agencies; however, given the lack of contamination found in prior studies of the DSM-H combined with differences in care provision at other sites/locations and the need for a large number of clusters when using this methodology, the investigators felt this method was the most likely to provide valid and reliable results. It is not possible to randomize by patient in HHC because patients are seen by care teams in a given geographic region. Patients in the performance improvement group will receive care from a care team who has received the DSM-H performance improvement program, and those in the control will receive usual care from a care team who has not received the performance improvement program. Patients at the study sites are only cared for by members of the same care team and therefore there is no potential for patients to receive a mixture of care teams.

### **4.2 Study Endpoints**

#### **4.2.1 Primary Study Endpoints**

Given that this is a dyadic, implementation science intervention, it is not appropriate to look at a single primary endpoint. There are therefore 3 primary endpoints that will be examined in this study. For the Aim 1 primary endpoint, PWD QOL, a 0.5 SD difference between the baseline and 60 day visit would be clinically meaningful based on prior studies and therefore considered a positive outcome. For the Aim 2 primary

CONFIDENTIAL

This material is the property of the NYU School of Medicine and Langone Medical Center. Do not disclose or use except as authorized in writing by the study sponsor  
 Interventional Template Version: 28 APR 2017

endpoint, informal caregiver QOL, given its rate of variability and floor and ceiling effects, a 0.5 SD difference between the baseline and 60 day visit would be clinically meaningful and therefore considered a positive outcome. For the Aim 3 primary endpoint, a 10% reduction in readmissions and ER visits at 60 days will be considered a clinically meaningful positive outcome. This would result in 220 fewer ER visits and 63.8 fewer admissions per 1000 patients based on prior evidence.

#### 4.2.2 Secondary Study Endpoints

Aim 1 secondary endpoints include individual BPSDs, pain, antipsychotic use and analgesic use. These endpoints were chosen secondary to their relationship to QOL and caregiver QOL as noted above in sections [2.1.1](#) and [2.1.2](#) as well as their interrelationship as noted in [section 2.1.3](#).

Aim 2 secondary endpoints include informal caregiver burden, depression, and health, which as noted in section [2.1.4](#).

Aim 3 secondary endpoints include outpatient visits and primary care provider contacts. These endpoints are included as BPSDs and pain are both indicators of additional concerns amongst caregivers and can increase burden due to the coordination that is required of caregivers.

#### 4.2.3 Exploratory Endpoints

In this study we will explore both sub-group analysis by gender, race/ethnicity, health literacy, and high and low symptom individuals.

### 5 Study Enrollment and Withdrawal for PWD-Caregiver Dyads

#### 5.1 Inclusion Criteria

1. PWD over the age of 65
2. Admitted to one of the three HHC agencies
3. The patient and family caregiver speak English and/or Spanish.
4. The informal caregiver is ≥18 years of age and manages the PWD's care for at least 8 hours per week.
5. Patients who score ≥6 on the Quick Dementia Rating Scale (at least mild impairment).
6. PWD and the caregiver have internet connection.

#### 5.2 Exclusion Criteria

An individual who meets any of the following criteria will be excluded from participation in this study.

1. Patients with a separate Axis 1 diagnosis other than forms of dementia, depression or anxiety.
2. PWD residing in assisted living facilities or board and care homes
3. PWD solely receiving infusion or home health aide services.

#### 5.3 Vulnerable Subjects

This research will be performed exclusively with cognitively impaired subjects and their informal caregivers. The research is specifically focused on whether the intervention improves the quality of care and quality of life for persons with dementia and their caregivers. It is therefore necessary to work with this vulnerable population. All patients in this study will be cognitively impaired, and some may lack the capacity to consent. These patients will all be included in this study. Capacity will be assessed at baseline as described in [section 5.4](#) below. They will not be monitored over the study period as dementia is a chronic, progressive disease there is no reasonable expectation that the PWD would have a capacity status change in such a short period of time (60 days). Should the person with dementia subject become distressed from participating in the study, they will be withdrawn from the study.

CONFIDENTIAL

## 5.4 Strategies for Recruitment and Retention

A centralized referral system will be customized to each of the three HHC agency's organizational structure and workflow. Each agency will determine which staff will be designated as the point of contact (POC) to submit patient referrals to the DSM-H research team. The method of referral will differ among agencies based on each organizational workflow. Each HHC agency accepts new referrals for patient admission through an intake process prior to the patient meeting with a nurse to initiate start of care (SOC). The nurse who completes the patient's admission visit, administers an OASIS assessment and OASIS cognitive screen or administers a mini-cog test for the patient's SOC report. The HHC agency's POC will review patient information obtained through intake and the SOC report. New admissions who are aged 65 years and older with a diagnosis of dementia or cognitive impairment, and who reside in a private residence will be referred to the DSM-H research study. Referral submissions will be received via REDCap, encrypted transfer, or secure email based on agency and NYU guidelines. If sent by encrypted transfer or secure email, the research coordinator or project director will upload the referral information directly into redcap, the study log.

Each agency has determined how their centralized referral system will be facilitated as noted below:

**New Jersey site (VNAHGX)** there will be a single point of contact in their research/innovation group who will run twice-daily reports of persons with dementia newly admitted to the agency who live in a private residence. Reports are based on the nurse's SOC report submitted at the end of the day.

**Utah site (CNS)** there will be a single point of contact within the agency who will generate a daily report of persons with dementia newly admitted to the agency who live in a private residence. The report will be based on the nurse's SOC report and made available to designated study staff or care team office referral specialist for referral submission.

**Florida site (FIRSTSTAT)** there will be a single point of contact within the agency who will generate a daily report of persons with dementia newly admitted to the agency who live in a private residence. The report will be based on the nurse's SOC report and made available to designated study staff or care team office referral specialist for referral submission.

Persons with dementia who are newly admitted into each HHC agency will be included in an "opt-out" referral process. Admission packets, provided to those who have been identified as meeting DSM-H inclusion criteria, will include a DSM-H research study information card. The DSM-H info-card provides an overview of the research study, the duration of participation, contact information for the research coordinators, as well as, ways in which the patient and caregiver can opt out from being contacted.

In follow up to the patient referrals received by each agency, the research team will contact the patient and/or caregiver to introduce them to the research study and to screen the referral for subject eligibility. To determine if the PWD's level of cognitive impairment meets eligibility for inclusion, the QDRS is administered to the caregiver who will rate the PWD's symptoms and behaviors. A PWD who scores  $\geq 6$  on the QDRS will meet eligibility for study inclusion as this score indicates mild impairment, similar to a score of  $<23$  on the MMSE. The research team will also inquire about whether the caregiver makes decisions on behalf of the PWD, or if there is a legally authorized representative who acts on the PWD's behalf. If the PWD has a LAR, then that representative's contact information will be obtained and the LAR will be included in the consent process. A virtual visit is scheduled for both the PWD and caregiver within 3 business days of the PWD's admission date so that additional information about the study can be provided and informed consent can be conducted. Weekend days and U.S. recognized business holidays are not counted as a business day. The PWD must have the capacity to consent in order to sign their consent form.

Capacity to consent will be determined using a standardized 3-question approach performed by the research assistant or project director. These individuals will receive training from the PI and Site PI in the form of two simulations prior to being allowed to consent using this procedure. In these simulations, one will have capacity and the other will not. They must correctly assess both simulations prior to being allowed

CONFIDENTIAL

This material is the property of the NYU School of Medicine and Langone Medical Center. Do not disclose or use except as authorized in writing by the study sponsor

to perform the consent process. This standardized approach has been shown to be valid for use by research assistants with PWD. The three questions that will be asked after reviewing the study consent form are: 1) What is the purpose of the study, 2) What are the risks, and 3) What are the benefits. If the initial response is vague or suggests misunderstanding, the interviewer re-explains or clarifies the question without redisclosing information about the study. The interviewer scores the answer to each question as either 0 (incapable) 1 (questionable) or 2 (capable). Definitions of these are as follows: *"2-point score reflects clear understanding of the disclosed material, a 0-point score reflects definite misunderstanding of the disclosed material, and a 1-point score reflects either partial but less than fully adequate understanding or, if this persists even after prompting for clarification, an uncertain level of participant understanding."* The score is then totaled and a score of less than 3 is considered to not have capacity. This method has a high level of sensitivity and specificity and is more accurate than using other methods including the mini-mental status exam (MMSE).

This standardized process is accurate and objective. There is limited conflict of interest in having the study personnel perform this assessment as opposed to an independent assessor as the study could still recruit dyads through surrogate consent should a subject not have capacity, and the patient flow at the participating HHC agencies far exceeds the needs of this study thus limiting pressure to enroll on the part of the study staff.

In instances where a PWD does not have the capacity to consent, their enrollment will be contingent upon consent being provided by either their LAR or a legal surrogate as determined by their state of residence. Further, once consent on the behalf of the PWD has been acquired, the PWD will be asked to assent verbally and if able, by signature. If the PWD provides verbal assent but is unable to provide their signature due to disability (cognitive/physical), the researcher will note on the assent form that the PWD provided verbal assent but was unable to sign.

The legal surrogate will be verified by either the HHC agency or through written documentation. Should they not have written documentation of being an appointed surrogate, the law of the state of residence will determine the priority order for determining the surrogate, which is as follows:

Florida: spouse, adult child, parent, adult sibling, close friend

New Jersey: spouse, adult child, parent, sibling, close friend

Utah: spouse, adult child, parent, sibling, grandchild, grandparent, individual who is healthcare proxy

Because PWD in HHC are primarily homebound, tend to receive HHC for at least 60 days, with follow-up is provided through scheduled home visits, we do not anticipate significant retention problems. Additionally, the study burden is minimal, requiring approximately an hour per dyad at baseline and 60-days, and 20 minutes at the 15 and 30 days. Study staff will obtain detailed contact information for the PWD, caregiver, and where applicable proxy, will schedule the follow-up visits at the initial visit, email or text the visit schedule to the caregiver (based on caregiver preference; no PHI or PII included, see templates), and call 4 days and 1 day prior to each follow-up appointment to confirm and/or reschedule.

The greatest risks to retention are re-hospitalization and institutionalization, either for short-term post-acute rehabilitation after a re-hospitalization or long-term institutionalization for ADRD. Subjects are not required to attend the intermediate and final visits together. Efforts to accommodate the subjects' schedules will be considered in data collection. Phone interviews with the PWD and caregiver to collect participant survey data will occur for all time points. If both subjects are unavailable to complete an intermediate visit, the visit will be recorded as missed. To maintain subject retention, subjects will be terminated from the study only if the caregiver, as respondent, does not complete visit four.

Dyads will be enrolled starting in month 6 of year 1 and continuing through month 9 of year 4 (3 years, 3 months). Follow-up will continue through Month 2 of year 5. The investigators therefore anticipate recruiting 9 new dyads per month at all sites throughout the 4 years, with 5-6 through the VNA Health Group, 2-3 at the University of Utah and 1-2 at University of Miami.

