Population	
Dyad Population
 
Total Sample: 345 Dyads (345 PWD + 345 caregivers)  Sample at NYU Site (VNAHG): 207  Sample at University of Utah Site (CNS; Central Utah): 86  Sample at University of Miami Site (FirstStat; Southern Florida): 52  Sample Description: PWD and their informal caregiver dyads. PWD must be 65 or older and informal caregiver 18 or over; English or Spanish speaking; Informal caregiver is defined as spending at least 8 hours per week and had an established prior relationship (family, friend, neighbor).

Study Sites	
NYU (lead): 0 clusters  VNAHG: 12 clusters  University of Utah: 5 clusters  University of Miami: 3 clusters

Number of participants	
Dyads: 345 across all sites (see population)

Description of Study Procedure	
The DSM-H is a multi-component quality improvement program that consists of clinician training, patient- and family-centered assessment instruments, patient-caregiver dyadic centered care plans, a BPSD assessment and treatment algorithm, and caregiver teaching sheets. This study will examine outcomes of this quality improvement program.

Reference Therapy	
Usual Care

Key Procedures	
None

Statistical Analysis	
Time trend analysis using repeated measure multivariate mixed effects linear models (PROC MCM in SAS) for all non-utilization outcomes. Utilization outcomes will be analyzed through logistic regression for odds of hospitalization or ER visit and Poisson Count regression for total number of hospitalizations and ER visits. Both will use random effects to measure for clustering.

CONFIDENTIAL

This material is the property of the NYU School of Medicine and Langone Medical Center. Do not disclose or use except as authorized in writing by the study sponsor

Interventional Template Version: 28 APR 2017

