## 10.5 Sample Size

Power analyses were conducted using Optimal Design software. Given that this study is randomized at the cluster level, we must control for intra-class correlation, and have therefore calculated all power with an intra-class coefficient of .05, which is more conservative than the most recent clustered palliative care study and aligns well with prior community-based cluster trials. The Quality of Life in Alzheimer's Disease as the primary outcome measure in aim 1 has an average score of 33.1, standard deviation of 5.9. A .5 standard deviation difference in this measure would be clinically meaningful. Therefore, in a 2-sample comparison with a power of .80, an alpha of .05 and covariates that account for a cumulative 15% of the variance in outcome would require 15 dyads per cluster, and 20 clusters (10 per arm) at 60 days to detect a medium effect ( $\delta = .45$ ). For mixed effects linear models, the projected sample size will also allow us to detect a medium linear treatment effect ( $\delta = .45$ ) between groups in unadjusted analyses (assuming 15 dyads per cluster, 20 clusters, 4 observations, and an ICC = .05). Although there are no closed-form equations for calculating the power of linear models that include covariates, any non-zero correlation between covariates and the outcome will reduce the unexplained (error) variance thus increasing the statistical power of our tests, and reducing the minimum detectable effect size. As such, the detectable effect size estimated for the unadjusted analyses can be considered an upper bound estimate for the effect size detectable in adjusted analyses. **We will recruit until we have reached 15 completed cases in each cluster (N=300).** Conservatively anticipating a 15% dropout over the 60 days requires a **total recruitment goal of 345 dyads**. As almost 20,000 patients are seen each year in the three HHC agencies in this study, approximately 30% with ADRD, we do not expect any difficulty recruiting this sample, even with an unanticipatedly high rate of dyads declining to participate.

In addition, for fidelity monitoring, as discussed in section [6.1.6.1](#), we will consent **300 clinicians** at the participating HHC agencies on usual care and quality improvement care teams to complete fidelity monitor by performing the DSKA survey. These clinicians are not study subjects but will be consented as they are

CONFIDENTIAL

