## 10.6 Measures to Minimize Bias

### 10.6.1 Enrollment/Randomization/Masking Procedures

As randomization is done at the cluster (care team) level, this will only be performed at the beginning of the trial. The study statistician will perform the randomization utilizing SAS 9.4 stratified by agency. The PI will relay to the home care agencies which teams will serve as quality improvement program teams or control teams. The study RAs, study project director, and site-PIs will all be blinded to the assignment. Teams will be randomized in strata by agency and geographic location to ensure like care teams are assigned to each condition. Subjects will be assigned through usual practice to the care team that serves the geographic area they live in. We will sequentially recruit individuals as they are referred from agencies following the very clear, straightforward method described above in section [5.4](#).

Clinicians will be enrolled sequentially if they are eligible and all study personnel with the exception of the lead site PI and study statistician will be blinded as to the assignment of the clinicians within a performance improvement or usual care team.

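### At Utah and Florida, agency office staff who are not required to be blind may submit referrals after teams are randomised, and no arm-wise count would reveal omissions

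*Combined protocol and SAP*

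**What the plan says.** Section 5.4 sets one referral rule for all three agencies: new admissions aged 65 or over, with dementia or cognitive impairment and living in a private residence, are to be referred. Submission differs by site.

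- **New Jersey:** "there will be a single point of contact in their research/innovation group who will run twice-daily reports". No care team office is named in the chain.
- **Utah and Florida (same wording):** one agency contact produces a daily report, which is then "made available to designated study staff or care team office referral specialist for referral submission".

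Section 10.6.1 places randomisation of teams at the start of the trial only. Section 4.1 says: "The study PI will relay to the agencies which teams will serve as intervention or control". The blinded roles in 10.6.1 are the RAs, the project director and the site-PIs; no agency office role is listed. Enrolment depends on what is submitted: "We will sequentially recruit individuals as they are referred from agencies".

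Section 9 makes the lead-site PI responsible for seeing that prospective subjects are targeted appropriately and completely. Under 10.6.1 that person knows the allocation.

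**The concern.** In a cluster trial that recruits after randomisation, whoever decides which eligible people reach the study team should either not know the arm or have no room to choose. At Utah and Florida the plan permits a submitter in the care team's own office, employed by an agency that has been told the arms. If that person passed on different kinds of dyads in the two arms, by severity, engagement or caregiver strain, the arms would differ in prognosis before any effect of DSM-H. Quality of life and utilisation could both be affected. Blinded RAs would not notice at the point of entry, because they meet only the submitted names.

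This step is separate from the admitting nurse's cognitive findings. Those determine who is on the report; this determines who on the report is submitted.

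**Working it through.** **1. How far the route reaches.** The Protocol Summary gives "VNAHG: 12 clusters", "University of Utah: 5 clusters" and "University of Miami: 3 clusters".

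- Teams: 12 + 5 + 3 = 20, matching section 10.5. Utah and Florida: 5 + 3 = 8, and 8/20 = 40%.
- Enrolled dyads (5.6): 86 + 52 = 138, and 138/345 = 40%.
- Complete dyads (5.6): 75 + 45 = 120, and 120/300 = 40%.

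**2. Who knows the arm, and who checks.**

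- The agencies know (4.1, 10.6.1). The referral specialist is agency staff and is not among the blinded roles. Knowledge of the arm is therefore possible, but no section says that the specialist is told.
- Referral of eligible admissions is mandatory (5.4). No section compares the report with what was submitted.
- QDRS screening by the research team (5.4, 7.2.1) tests those submitted, not those left out.
- The DSMB sees recruitment data by site (8.8.3.1.2), not by team or arm, and not against the reports.
- The targeting check in section 9 has no stated method and is done by a person who knows the arms.

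**3. Would missed names show up as slow enrolment?** Section 10.5 cites almost 20,000 patients a year, about 30% with ADRD; section 5.4 gives 3 years 3 months of enrolment. 20,000 × 0.30 × 3.25 = 19,500 patients, and 345/19,500 = 1.8%. This covers all three agencies together and comes before other eligibility limits. Targets could be met with many listed names never submitted.

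**4. The plan's own power.** Section 10.5 states that the design "would require 15 dyads per cluster, and 20 clusters (10 per arm) at 60 days to detect a medium effect" (.45 SD), with ICC .05, alpha .05 and power .80. Taking the test as two-sided, which the section does not state:

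- SE = sqrt(4 × (ICC + (1 − ICC)/m)/J) = sqrt(4 × (.05 + .95/15)/20) = .1506 SD.
- Noncentral t with 18 df: power .807 and minimum detectable effect .446. The stated .80 and .45 are reproduced (unadjusted).

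**5. Illustration only.** The documents give no size for any selection effect. Assume that filtering shifts QOL-AD between arms by d SD in all 8 teams, that these teams split equally between arms, that the other 12 are unaffected, and that the shift carries fully into the unadjusted 60-day comparison. Then pooled bias = .40 × d. In QOL-AD points (SD 5.9, section 10.5), and with the rejection rate when DSM-H has no effect:

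- d = 0.1: bias .04 SD, 0.24 points, 9% of .45; type I error 5.7%
- d = 0.2: bias .08 SD, 0.47 points, 18% of .45; type I error 8.0%
- d = 0.3: bias .12 SD, 0.71 points, 27% of .45; type I error 11.7%

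If only half of the 8 teams in each arm used the specialist route, these biases would halve (at d = 0.3: .40 × 0.5 × 0.3 = .06 SD). If none did, they would be zero.

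**The case against.** The case on the other side is substantial.

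- **The rule leaves no discretion on paper.** A reader might infer that the submitter is free to choose from the report. Section 5.4 does not support that: all who meet objective criteria are to be referred, patients enter by an opt-out process, and recruitment is sequential. What is missing is a check that the rule was followed. This stands, and it narrows the point.
- **Knowledge of the arm is inferred.** A reader might infer that the specialist, or each team's office, is told the assignment. The text says only that the agencies are told. The clinicians trained are nurses and therapists (6.1.2); no office role is mentioned. This stands.
- **The route is optional.** Study staff are the other choice in the same sentence, so 40% is the most that could be affected by this step.
- **A completeness check exists.** The lead-site PI's duty in section 9 is a safeguard, but a partial one, since that person knows the arms and no method is given.
- **The New Jersey contrast is soft.** That contact also works for an agency that knows the arms, and 5.4 has each agency's contact review patient information. This stands, and it is why the count reconciliation should cover all three agencies.
- **Baseline data help.** QOL-AD and caregiver QOL are measured at day 0, baseline differences are tested, and analyses are repeated with baseline covariates (10.4.1). A measured shift would be visible and partly absorbed. Unmeasured prognosis would remain, and the unadjusted comparison comes first.

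**Conclusion.** The plan allows referrals in up to 8 of 20 teams (138 of 345 planned dyads) to pass, after randomisation, through a person who is not required to be blind and who may know the arm. Because the only completeness check lies with someone who knows the allocation, arm-related omissions could go unnoticed. That is the extent of the finding.

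A reader might go on to infer that the trial is biased, or that its false-positive rate is about 6 to 12%. The documents do not support either. They show no filtering, and those rates rest wholly on an assumed 0.1 to 0.3 SD shift, in a consistent direction, with the optional route used in all 8 teams. Nor should 8 of 20 be read as a firm boundary, since the New Jersey contact is agency staff too. This is a cheap improvement of low to moderate priority.

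**What to change.** In section 5.4, for both Utah and Florida, delete the alternative that names the care team office referral specialist. State that the agency contact's full report goes to designated blinded study staff, who submit every listed patient. The study-staff route is already in the same sentence.

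At all three agencies, keep a log by team of report entries against submissions, with a reason for any omission. Have someone outside the blinded data-collection staff compare the counts by arm. The study statistician would fit, since that role already holds the allocation and does not collect data (4.1). If enrolment is advanced and past reports were kept, the same comparison can be made retrospectively and would show whether omissions differed by arm.

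Cost: one phrase at each of two sites, a short log, a little more work for study staff, and secure access to reports at two agencies. Sample size and analysis are unchanged.
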